Protocol Full Title:

Tear film SARS-nCoV-2 detection in symptomatic and pauci-symptomatic patients.

Protocol Acronym/short title:

Eye-COVID

Version and date of protocol:

V8.0 dd 16-09-2020

Principal Investigator:

Name: dr. [name]

Address: UZ Leuven campus Gasthuisberg, Ophthalmology Department, [name]

[contact]

Email: [contact]

Contact:

[figure not shown]
Name: dr. [name]

Address: UZ Leuven campus Gasthuisberg, Ophthalmology Department, [name]

[contact]

Email: [contact]

Signature Principal Investigator

[name] MD

Principal Investigator

Date: 16-09-2020

Tear film SARS-nCoV-2 detection in symptomatic and pauci-symptomatic patients.

Eye-COVID V8.0 dd 16-09-2020

Pagina 1 van 23

[figure not shown]
Protocol approved by

Prof. dr. [name] MD PhD
Head of the Department of Ophthalmology
(Sub Investigator)

[figure not shown]
[name], MD
(Sub Investigator)

[name] MD PhD
(Sub Investigator)

[name] [name] MD PhD
(Sub Investigator)

Tear film SARS-nCoV-2 detection in symptomatic and pauci-symptomatic patients.

Apotheker klinisch bioloog [name]
(Sub Investigator)

A handwritten signature in blue ink, appearing to read "[name]".

[name] PhD
(Counseling Sub Investigator)

Tear film SARS-nCoV-2 detection in symptomatic and pauci-symptomatic patients.

Eye-COVID V8.0 dd 16-09-2020

Pagina 3 van 23

Title of clinical trial	Tear film SARS-nCoV-2 detection in symptomatic and pauci-symptomatic patients.
Protocol Short Title/Acronym	Eye-COVID
Funding	R95328
Principal Investigator	Dr. [name]
Sponsor	University Hospitals Leuven [name]
Sponsor Reference Number	S 64002
Purpose of clinical trial	To investigate the presence of SARS-nCoV-2 in the tear film of symptomatic and pauci-symptomatic SARS-nCoV-2 positive patients.
Trial Design	Exploratory study using biological samples
Summary of eligibility criteria	
 • ≥ 18 years old. • Willing to undergo sampling of the conjunctiva. • Willing to fill in a questionnaire. • Fluent in written and verbal Dutch. • Capable of giving informed consent. • Part 1 only: positive test for SARS-nCoV-2 on a nasopharyngeal swab.

Tear film SARS-nCoV-2 detection in symptomatic and pauci-symptomatic patients.

This is consistent with the Google Trends analysis. The most common coronavirus related search queries are loss of smell, fever, and chills. While nasal congestion and diarrhea were fifth and sixth on the search terms. It is the fourth most searched term - eye pain - that has now caught the eye (quite literally) of researchers as it could be a possible symptom of the COVID 19 (5).

Independent of the severity of respiratory symptoms, the presence of the virus in tears (positive for SARS-nCoV-2 via qPCR assessment) has been described in patients with conjunctivitis (6,7). This in line with earlier results during the SARS epidemic of 2003 (8). However, the presence of SARS-nCoV-2 in tears, implies that the disease might possibly be transmitted via this body fluid, especially during certain specific procedures such as pneumotonometry and excimer refractive laser surgery. Specific to these procedures is the use of a jet of air and a laser beam, transforming tears to **small droplets** (9–11).

To further investigate the potential spread of the virus through tears, we aim to set up a two-part study. The first part of our study is to confirm the detectability of the SARS-nCoV-2 in the tear film of **symptomatic** patients. Patients admitted at our University Hospital Leuven, Belgium with a positive nasopharyngeal swab for SARS-nCoV-2 will be informed about our project. They will be asked to sign an informed consent for serial swabbing of the conjunctiva every 3 days until the end of their hospitalization.

A conjunctival swab is chosen above other methods such as Schirmer's test since a swab is besides faster also easier to teach and requires less contact with the volunteer. The serial swabbing will not only be informative on the duration of viral shedding in the tears, but also on the timing that SARS-nCoV-2 becomes detectable with qPCR in the tear film. Furthermore, a questionnaire (*cf. Addendum A*) will be used to search for correlations between SARS-nCoV-2 positive conjunctival swabs and the patient's disease stage (including results of routine blood samples), presence of ocular symptoms and/or

Tear film SARS-nCoV-2 detection in symptomatic and pauci-symptomatic patients.

perception of anosmia and/or ageusia. Especially this anosmia part might be interesting. A correlation between anosmia and a positive PCR in the tear film is suspected based on the connection between the nose and eyes via the nasolacrimal duct and the proximity of the olfactory nerve to the orbital cavity and eye.

The other parts of our study aims to confirm the detectability of the SARS-nCoV-2 virus in the tear film of **pauci-symptomatic** volunteers, more specifically patients presenting at the emergency room of the University Hospitals Leuven, health care workers with mild symptoms and patients admitted for other reasons though SARS-nCoV-2 positive.

Presumably, the rate of pauci-symptomatic carriers is higher within health care workers compared to the general population. Emergency patients and health care workers are preferred over pauci-symptomatic pre-operative patients, since prevalence of SARS-nCoV-2 is low in these pre-operative patients (data UZ Leuven Laboratory Medicine (1 June 2020): prevalence of around 0.2%). Similar to the symptomatic patients, all volunteers will be informed about our project and asked to sign an informed consent for simultaneous swabbing of the conjunctiva and the nasopharynx. The pauci-symptomatic group will include only volunteers already listed for nasopharyngeal swabbing based on their symptoms (to avoid unnecessary use of nasopharyngeal swabs). By testing pauci-symptomatic volunteers, we intend to better substantiate current guidelines in ophthalmology practice. Mostly “deemed-healthy” patients visit outpatient clinics, but when carrying the virus, they are the highest risk of contaminating health care workers. Proving presence of (viable) SARS-nCoV-2 virus in the tear film of pauci-symptomatic volunteers might change our ophthalmology practice in the long run. Furthermore, we want to compare results of both the ocular and nasopharyngeal swab (both positive for SARS-nCoV-2; both negative for SARS-nCoV-2; discordant results, with either eye or nasopharynx positive and the corresponding sample negative for SARS-nCoV-2). For patients with discordant results, we purpose to identify potential correlations between disease-severity and detection of SARS-nCoV-2 in different body fluids by using the same questionnaire mentioned above (*cf. Addendum A*). The difference in RNA viral load (by means of quantitative result (Cycle threshold (Ct) of the SARS-CoV-2 PCR) in the tears of different patients at different moments in time (i.e. the assessment of the evolution of quantitative result) will be indicative for the transmissibility of the virus. However, to evaluate genuine transmissibility, swabs positive for SARS-CoV-2 via qPCR will be sent to the REGA institute (i.e. the Laboratory of [name]) for **viral culture and detection of subgenomic (sg) RNA**. This is in contrast to most previously published studies focusing only on the detection of SARS-CoV-2 RNA by PCR. SARS-CoV-2 PCR is not able to differentiate between live or dead virus (6–8). It is important to make that difference in order to draw conclusions on potential transmission of the virus by tears. Detection by culture indicates if viable virus is present in the sample. Detection of sgRNA is an indicator for replication of the virus. The viability of the virus collected from tear samples will determine the risk of spreading the virus via tears.

Tear film SARS-nCoV-2 detection in symptomatic and pauci-symptomatic patients.

This research project intends to provide a more thorough understanding of the presence of this new virus in the tear film of SARS-nCoV-2 positive patients. Furthermore, it could provide insight in the timing of the contagiousness of tears and highlights correlations with other signs and symptoms.

[figure not shown]

Figure 1: study design.

2. Trial objectives and design

Primary outcome measures

- 1) The presence of SARS-nCoV-2 in the tear film of symptomatic and pauci-symptomatic SARS-nCoV-2 positive patients.
- 2) Correlations between SARS-nCoV-2 in the tear film and mild (like anosmia, ageusia, upper and lower respiratory tract infection) or severe symptoms (as pneumonia, need for hospitalization) of COVID-19.

Secondary outcome measures

- 1) The stage of disease when SARS-nCoV-2 becomes detectable in the tears.
- 2) Duration of shedding of SARS-nCoV-2 RNA in the tears.
- 3) Difference in RNA viral load (by means of quantitative result (Cycle threshold (Ct) of the SARS-nCoV-2 PCR) in tears of different patients at different moments in time in order to estimate potential difference in transmissibility of the virus by tears.
- 4) Assessment of evolution of quantitative result (Cycle threshold (Ct)) of the SARS-nCoV-2 PCR over time within conjunctival SARS-nCoV-2 PCR positive patients
- 5) Searching for a correlation between both quantitative and qualitative results of SARS-nCoV-2 PCR on the nasopharyngeal and conjunctival swab (both positive for SARS-nCoV-2; both negative for SARS-nCoV-2; discordant results, with either eye or nasopharynx positive and the corresponding sample negative for SARS-nCoV-2).

Tear film SARS-nCoV-2 detection in symptomatic and pauci-symptomatic patients.

- 6) Exploring the possibility of testing the tear film on SARS-nCoV-2 as a screening tool for early disease.
- 7) Exploring the replication of the SARS-nCoV-2 virus, by differentiating between death and alive SARS-nCoV-2 virus through sg RNA-testing and tissue culture.

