3.1 Inclusion criteria

- Subject needs to be above 18 years old.
- The subject is willing to undergo sampling of the conjunctiva.
- The subject is willing to fill in a questionnaire.
- The subject is fluent in written and verbal Dutch.
- The subject is capable of giving informed consent.
- Applicable for part 1 only: the subject test positive for SARS-nCoV-2 on a nasopharyngeal swab. The time window between a positive nasopharyngeal swab and the first conjunctival swab may be no more than 3 days.
- Applicable for part 2 only: mild symptoms of COVID-19 including symptoms of upper or lower respiratory tract infection and/or any body temperature elevation (criteria Sciensano for testing healthcare workers (April 12 2020)) without the need for hospitalization.

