4.1 Summary of visits

Part 1: Serial sampling of symptomatic patients

Sampling will take place at the “rampen unit” of the University Hospitals Leuven, Belgium. Once the patient is admitted and tested positive for SARS-nCoV-2 on nasopharyngeal swab, conjunctival sampling will take place every three days until the day of discharge. The time window between a positive nasopharyngeal swab and the first conjunctival swab may be no more than 3 days.

Part 2: Single sampling of pauci-symptomatic patients

Sampling will take place at the emergency department of the University Hospitals Leuven, Belgium by the swab team. The sampling will not be repeated.

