7.2 Analysis

The statistical analyses will be performed using statistical software such as R-studio or SPSS. The Shapiro-Wilk test will be used for normality testing. Depending their distribution, continuous variables will be summarized as mean \pm standard deviation or median with interquartile range. Categorical variables will be summarized in absolute numbers and percentages. All statistical test will be significant if the P-value ≤ 0.05 .

Primary outcome measures

The presence or absence of the virus in the tears is the primary objective. A multivariate analysis will be used to interpret the questionnaire.

Secondary outcome measures

Tear film SARS-nCoV-2 detection in symptomatic and pauci-symptomatic patients.

For secondary outcome measures, we first have to indicate the different disease stages. We define them as early, intermediate and late stadium, respectively indicated by onset disease symptoms (cough, fever, fatigue, myalgia and lesser reported symptoms such as headache, diarrhea and abdominal pain, ageusia and anosmia, conjunctivitis), development of chest pains and dyspnea with need for hospitalization and eventually development of SARS and need for ICU administration (12). We also define a remission stage in which symptoms start to decline.

For investigation of the disease stage in which the SARS-nCoV-2 becomes detectable in the tears we aim to use an ANOVA analysis.

8. Quality assurance

To assure maximal quality and reproducibility, the trial protocol will be followed rigorously.

9. Direct access to source data and documents

Only data gathered in the context of the trial will be used.

10. Ethics and regulatory approvals

The trial will be conducted in compliance with the principles of the Declaration of Helsinki (2008), the principles of Good Clinical Practice and in accordance with all applicable regulatory requirements. This protocol and related documents will be submitted for review to Ethics Committee of the University Hospitals Leuven.

The Study will be conducted only on the basis of prior informed consent by the Subjects to participate in the Study. We shall obtain a signed informed consent form (ICF) for all patients prior to their enrollment and participation in the Study in compliance with all applicable laws, regulations and the approval of the (local) Ethics Committee, if required. We shall retain such ICFs in accordance with the requirements of all applicable regulatory agencies and laws.

11. Data Handling

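### Secondary outcome 1 asks when tears become positive, but single Part 2 swabs and Part 1 first-swab positives cannot show it, and stage at first positive swab largely reflects the recruiting part

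*Combined protocol and SAP*

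**What the plan says.** The first secondary outcome in section 2 is "The stage of disease when SARS-nCoV-2 becomes detectable in the tears". Section 1 says that the serial swabs will be informative "on the timing that SARS-nCoV-2 becomes detectable with qPCR in the tear film".

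The sampling schedule is in section 4.1. Part 1 patients are swabbed once admitted and nasopharyngeal-positive, then every three days until discharge: "The time window between a positive nasopharyngeal swab and the first conjunctival swab may be no more than 3 days". For Part 2, "The sampling will not be repeated".

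Section 7.2 defines the stages: "We define them as early, intermediate and late stadium, respectively indicated by onset disease symptoms". The intermediate stage is marked by "development of chest pains and dyspnea with need for hospitalization", and the late stage by SARS and need for ICU. There is a fourth stage: "We also define a remission stage in which symptoms start to decline".

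Part 1 recruits on a non-ICU ward (section 2.1). Part 2 requires mild symptoms under the "criteria Sciensano for testing healthcare workers (April 12 2020)) without the need for hospitalization" (section 3.1).

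The only analysis named for this outcome in 7.2 is ANOVA. No rule is given for patients positive at their first swab, or for whether and how Part 2 contributes.

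**The concern.** To say at which stage virus becomes detectable, one needs a negative sample followed by a positive one, or at least bounds on when the change happened. Neither part takes a tear sample before recruitment. If the stage at the first positive swab is used as the stage of onset, the result mostly restates the eligibility criteria: inpatients come out as intermediate and mildly ill volunteers as early. A different test in place of ANOVA would not help, because the value being analysed is itself unobserved.

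Section 1 hopes for insight into when tears are contagious and says that the pauci-symptomatic results might change ophthalmology practice. An onset stage that really marks admission would understate how early tears can be positive.

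**Working it through.** The plan states no figure for this outcome, so there is none to reproduce. The main check sets the sections side by side.

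**What each swab pattern shows about onset**

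| Patient | Information on onset | Stage at first positive swab |
|---|---|---|
| Part 2, positive | At or before the only swab | Early by eligibility, unless remitting |
| Part 1, positive at swab 1 | At or before swab 1 (left-censored) | Intermediate by setting, unless remitting |
| Part 1, negative then positive | Between two swabs about 3 days apart | Stage within that interval |
| Part 1, never positive | Not yet positive, already cleared, or never tear-positive | None |

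Only the third row observes the change. Leaving false-positive PCR aside, a first positive swab cannot come before the true change, so using it as the onset date errs in one direction only: late.

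**Size in Part 1 (illustration; every timing is an assumption)**

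Days are counted from symptom onset.
- Tear onset T: normal, SD 1.5, mean as in the table below.
- Shedding D: exponential, mean 7 or 14 days.
- Admission A: normal, mean 7, SD 2.5.
- First swab F = A + a uniform delay of 0 to 3 days. The 3-day limit is from section 4.1, although the plan counts it from the positive nasopharyngeal swab.
- Stay: exponential, mean 8 days. Swabs every 3 days (section 4.1) until discharge.
- A swab at time t is positive if T ≤ t ≤ T + D. Delay = time of first positive swab − T.

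Simulated results among patients ever observed positive:

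| Mean tear onset | Already positive at swab 1 | Mean delay | True onset before admission |
|---|---|---|---|
| Day 2 or 5 | 90-99% | 3.3-6.0 days | 72-95% |
| Day 8 | 69-70% | about 2 days | 39-45% |
| Day 10 | about 48% | about 1.6 days | 20-23% |

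The last two entries in the final column also cover a less variable shedding time (gamma, shape 4).

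A wider grid used mean tear onset from day −1 to 12, mean admission from day 5 to 10 (SD 2 each), mean shedding of 10 days and mean stay of 9 days. The share positive at swab 1 then ran from 5% to 100%. The share depends on how tear onset falls relative to admission, which the documents do not give.

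**Never-positive patients**

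With mean tear onset at day 2 or 5 and exponential shedding, 22-57% of all patients turn positive and clear (T + D < F) before the first swab. They make up 78-99% of those never observed positive. If gamma shedding is included as well, the ranges are 6-57% and 51-99%. In these scenarios most never-positive patients had their onset before the first swab, not after the last.

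**The case against.** The strongest reply is that the plan is silent rather than wrong. No section says that the stage at first swab will be assigned as the onset stage, or that Part 2 positives will be scored as early onset. Sections 1 and 2.1 tie timing to the serial swabs, and section 1 presents Part 2 as a study of detectability and of agreement between eye and nasopharynx. This stands: a reader might infer that Part 2 will be scored as early, but the documents do not say so. The gap remains, because outcome 1 is not limited to Part 1 and 7.2 has no rule for first-swab positives.

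A reader might also infer that recorded stage is fixed entirely by recruitment, or that the answer would be wrong whatever the truth. The documents do not support that. Remission depends on symptoms and not on setting. The intermediate stage also names chest pains and dyspnea, which Addendum A dates individually, and Part 1 eligibility does not require them. Part 2 includes inpatients admitted for other reasons. Negative-then-positive patients do bracket their onset.

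It is likewise tempting to conclude that about nine in ten positives are already positive at swab 1. That rests on placing mean tear onset before mean admission. With later onset the share falls to about half, or lower on the wider grid.

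Finally, this is a secondary outcome of an exploratory study, and the hoped-for insight into timing is worded cautiously. This limits the weight of the point but does not answer it.

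**Conclusion.** The point holds as a limit on what outcome 1 can show. Part 2 cannot observe tears becoming positive, and Part 1 can do so only in patients negative at the first swab. Stage at first positive swab would largely, not wholly, reflect the part of recruitment, and if read as onset it can only be late. This rests on the text alone.

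The size does not. Under the stated assumptions, roughly 48-99% of ever-positive Part 1 patients are positive at swab 1, with a mean delay of about 1.6 to 6 days, and other timings widen the range. The presence-or-absence primary outcome is unaffected. The change should be made, but the point is not critical to the study.

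**What to change.** In sections 2 and 7.2:

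1. Redefine outcome 1 as the proportion tear-positive by stage at sampling and by days since symptom onset, shown separately for Parts 1 and 2.
2. Describe onset only for Part 1 patients with an observed negative-then-positive change, bracketed by the two swab dates, and state how many there are.
3. Report Part 1 first-swab positives as having onset at or before the first swab. Do not assign stage at first swab as onset stage.
4. Report never-positive patients as a separate count. Do not right-censor them for onset: they may have cleared before the first swab or may never become tear-positive, and right-censoring those who had cleared would push estimated onset late.

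The cost is wording. Addendum A already records the first day of symptoms, and no swab or visit is added. One source needs naming: Addendum A asks when symptoms began, not when they eased, so remission at a given swab must come from elsewhere. The downside is that few changes may be observed. Onset information will then be sparse, and it will apply only to patients still negative at the first swab.

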2.1 Preparation, organization and management of this exploratory study

Part 1: Serial sampling of symptomatic and confirmed positive patients

Patients will be informed about the study by a health care worker at a non-ICU unit (“rampen unit”) of the University Hospitals Leuven, Belgium.

In case a candidate is interested in participating and tested positive for SARS-nCoV-2 on his/her nasopharyngeal swab, he/she will be informed about the study goals by the same health care worker. The volunteer will receive an information letter and a copy of the informed consent to take home.

Study procedure

After signing the informed consent, each patient will be asked to fill in a questionnaire (cfr. *Addendum A*).

The simplicity of performing a conjunctival swab makes it possible **to implement in the daily routine** of health care workers, **avoiding additional waste of personal protective equipment.**

Conjunctival sampling will be performed on both eyes after the application of a drop of topical anesthesia (Minims® Oxybuprocaine Hydrochloride 0.4%, Bausch and Lomb, Aubenas, Frankrijk). A timed 5 minutes will be in between application of the drop and the sampling. The sampling will be performed by a trained nurse and/or medical student and/or resident after proper training of correct sampling (cfr *Addendum B*).

Each eye will be sampled with a single, sterile, nylon, flocked swab (FLOQSwabs®; Copan, Brescia, Italy). This FLOQSwabs® is a **different** swab than the one used for routine nasopharynx SARS-nCoV-2 testing.

The sampling will be done from the nasal to temporal inferior conjunctival sac, the swab will be swirled in the opposite direction of the sampling itself.

The swabs will be placed in a tube with universal transport medium (UTM) and transferred to a -80°C freezer until further processing.

The conjunctival swab will be tested for SARS-nCoV-2 presence by making use of in-house reverse transcription real-time polymerase chain reaction (RT-PCR) designed for routine diagnostics targeting specific SARS-nCoV-2 genes in the clinical laboratory of the University Hospitals Leuven or at the REGA institute (laboratory of [name]).

Tear film SARS-nCoV-2 detection in symptomatic and pauci-symptomatic patients.

Serial sampling

Sampling will be repeated every 3 days to evaluate if PCR becomes positive during the course of disease and to monitor the duration of detectability of the virus in tears.

Part 2: Single sampling of pauci – symptomatic patients

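### Duration of RNA shedding in tears (secondary outcome 2) has no clearance rule, no two-eye rule and no analysis that allows for unseen starts and ends, so the default summary would partly reflect length of stay

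*Combined protocol and SAP*

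**What the plan says.** Section 2 gives the outcome in one line: "Duration of shedding of SARS-nCoV-2 RNA in the tears". Section 2.1 (Part 1, serial sampling) gives the schedule and one purpose: "Sampling will be repeated every 3 days to evaluate if PCR becomes positive during the course of disease". The other purpose is "to monitor the duration of detectability of the virus in tears". Section 4.1 sets the end of sampling: "conjunctival sampling will take place every three days until the day of discharge". The first eye swab may come up to 3 days after the positive nasopharyngeal swab (sections 3.1 and 4.1). For Part 2, section 4.1 states: "The sampling will not be repeated".

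At each visit, "Conjunctival sampling will be performed on both eyes", each eye with its own swab. No section says whether one positive eye makes the patient positive or whether both must be negative for clearance.

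Section 7.2 names one method for one secondary outcome: ANOVA, for secondary outcome 1, "The stage of disease when SARS-nCoV-2 becomes detectable in the tears". Continuous variables in general are summarized by mean and SD, or by median and interquartile range. Censoring is not mentioned. Addendum A records the date of first symptoms.

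**The concern.** Only Part 1 can inform duration, because Part 2 has a single swab. In Part 1 the observation window opens after admission and closes at discharge. A patient already positive at the first swab has no observed start of tear positivity. A patient still positive at the last swab has no observed end. Between those points, each change of status is known only to within 3 days.

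If observed positive time is treated as an ordinary continuous variable, as the general rule in section 7.2 would have it, the result mixes how long tears stay positive with how long patients stay in hospital. Two cohorts with the same shedding and different discharge practice would report different durations. Section 1 says the study is meant to inform ophthalmology practice, and this figure would be read as how long tears carry viral RNA.

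**Working it through.** The plan states no expected duration, length of stay or Part 1 sample size, so there is no figure of its own to reproduce.

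**1. From the schedule alone (no assumed values except no false-negative swab).** Take swabs at days 0, 3, 6, … after the first, ending at discharge on day L.

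- The last swab falls on day 3 × floor(L/3), so first-to-last positive time cannot exceed that. For L = 2, 5, 7, 10 and 12 the ceiling is 0, 3, 6, 9 and 12 days.
- With k positive swabs between two negatives, true duration lies between 3(k−1) and 3(k+1) days. For k = 1 that is 0 to 6 days, for k = 2 it is 3 to 9. First-to-last positive is always the lower limit.
- Seeing both ends needs at least three swabs (negative, positive, negative), so L of at least 6 days.

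**2. Dependence on stay (all inputs assumed).** Suppose every patient is positive at the first swab, remaining shedding is exponential with median 10 days (mean 10/ln 2 = 14.4), stay after the first swab is gamma with shape 3, the two are independent, and the swabs make no errors. Observed duration is last positive swab minus first swab.

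| Median stay (d) | Observed mean (d) | Observed median (d) | Still positive at last swab | Correlation with stay |
|---|---|---|---|---|
| 5 | 3.0 | 3 | 77% | 0.67 |
| 8 | 4.8 | 3 | 63% | 0.56 |
| 12 | 6.6 | 6 | 49% | 0.44 |
| 20 | 8.9 | 6 | 32% | 0.29 |

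Shedding is identical in all four rows. A Kaplan-Meier median of time to first negative swab, censored at the last swab, is 12 days in every row; the excess over 10 comes from the 3-day grid. With a true median of 5 days and a median stay of 20 days, only 15% are still positive at the last swab and the correlation with stay falls to 0.13.

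**3. A wider set of assumed inputs.** This model adds a lag from symptom onset to tear positivity.

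- Over 243 scenarios (mean shedding 7 to 21 days, mean stay 5 to 12 days, with varied lag, delay to first swab and shedding distribution), 21% to 95% of tear-positive patients were still positive at the last swab. Raising mean stay from 5 to 12 days multiplied the first-to-last mean by 1.6 to 2.5.
- Outside that grid, with mean shedding 3 or 5 days and mean stay 12 or 20 days, about 6% to 31% were still positive. Going from 12 to 20 days raised the first-to-last mean by less than a factor of 1.2.

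**4. False-negative swabs.** Suppose the first negative swab counts as clearance and each swab of a truly positive patient is positive with probability s, independently. A life table in patients positive at the first swab then estimates s² × S(6) at 6 days, because two further swabs must both be positive. With mean lag 4, shedding 10, delay 7 and stay 7 days, S(6) is about 53%. For s = 0.9, 0.8 and 0.7: 0.53 × 0.81 = 43%, 0.53 × 0.64 = 34%, 0.53 × 0.49 = 26%.

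**5. Discharge linked to recovery.** With an assumed correlation of 0.3 or 0.6 between shedding and stay (no lag, mean shedding 14 days), all-swab positivity at days 13 to 15 since onset was 48% or 59% against a true 39%. First swabs only gave 40% against a true 40% in both cases.

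**The case against.** The plan never says it will report first-to-last positive time, or that the mean or median rule applies to this outcome. That is correct. A reader might infer that the plan prescribes a biased statistic, but the documents do not support that. They leave the choice open, and the general rule is simply the only one in section 7.2 that would reach a duration.

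A reader might also infer that duration has no origin at all. That goes too far. Section 2.1 speaks of detectability in tears, so first tear PCR positivity is the natural start. The difficulty is that this start is often unobserved.

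A third tempting reading is that swabbing ends at ICU transfer, because recruitment is described as "Patients will be informed about the study by a health care worker at a non-ICU unit". The documents do not settle it. Sections 1 and 4.1 run the swabs to the end of hospitalization or to discharge, and the disease stages in section 7.2 include ICU. Against that, section 4.1 places sampling at the same non-ICU unit.

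The study calls itself exploratory and a pilot, and section 7.2 is equally silent on method for secondary outcomes 3 to 7. This limits the weight of the point. It excuses low precision, but not a quantity whose value depends on discharge practice. It is also a fair objection that full modelling of converters, or a delayed-entry model from symptom onset, would be more than such a study needs.

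**Conclusion.** Wrong as written, of minor to moderate weight, and confined to secondary outcome 2. The primary presence-or-absence result is not affected. Three gaps are plain in the text: no clearance rule, no rule for two eyes, and no named analysis for an outcome that is censored at both ends by design.

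The ceiling of 3 × floor(L/3) days and the 0-to-6-day range for a single positive swab follow from the schedule, given no false-negative swabs. Everything beyond that rests on assumed shedding, stay and test error. The simulated ranges illustrate the problem; they neither bound nor estimate the bias in this trial. If shedding is short and stays are long, the distortion is small. If most patients are still positive at their last swab, it is large. The documents do not say which case applies.

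**What to change.** Add to section 7.2:

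1. An uncensored mean or median of observed positive time will not be reported as shedding duration.
2. State the patient-level rule for positive and for cleared (one eye or both) and how a negative followed by a positive is handled. If a single negative counts as clearance, add a sensitivity analysis, since false negatives shorten the estimate.
3. For patients positive at the first swab, estimate time from that swab to clearance by a life table or interval-censored method, right-censored at the last swab, and label it remaining time. For patients who convert during the stay, give counts and the observed lower and upper limits of duration.
4. Alongside, report the proportion tear-positive by day since symptom onset (date already in Addendum A), labelled as prevalence and not duration. Give the numbers under observation and counts never positive, positive at first swab, converting, and still positive at last swab.
5. State that discharge may be related to recovery, so censoring may be informative. Repeat item 4 with first swabs only.
6. Clarify whether swabbing continues after transfer out of the non-ICU unit, reconciling sections 1, 2.1 and 4.1.

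If few patients are tear-positive, report only item 4 and its counts.

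The cost is wording and standard software, with no new swabs or data items. The downsides are wide intervals, a median that may not be estimable, and clearance before the first swab that stays unobserved. Part 1 size is not given. As assumed examples for item 4, 10 of 20, 25 of 50 or 50 of 100 positive in a window gives a 95% interval of 30–70%, 37–63% or 40–60%.
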